21.2 Exclusion Criteria

Subjects who meet any of the exclusion criteria at Visit 1 will be excluded from study participation and may be replaced. Exclusion criteria must be assessed by a study investigator who is also a clinician licensed to make medical diagnoses. Subjects will not be able to participate if they have any of the following:

1. Documented history of allergy or intolerance to components of the IMP, relevant radiologic contrast media, or local anaesthetics.
2. Is pregnant or lactating.
3. Has been taking corticosteroid medications routinely in the past 6 months or has received an epidural corticosteroid injection within 12 weeks of screening.
4. Has a BMI greater than 40 kg/m².
5. Has Diabetes Mellitus (Type 1 or Type 2) - prior confirmed HbA_{1c} or OGTT
6. [REDACTED]

- [REDACTED]
- [REDACTED]
- [REDACTED]
- [REDACTED]
- [REDACTED]
12. Has a history of significant leg pain unrelated to disc herniation that would significantly compromise assessment of back or leg radicular pain.
 13. Has radiological evidence of symptomatic disc herniation above L4-L5.
 14. Has radiological evidence of clinically significant foraminal stenosis at L4-L5 or L5-S1 or of clinically significant spinal stenosis, or spondylolisthesis (Grade 2 or higher). (Note, asymptomatic foraminal stenosis at other spinal levels is not excluded).
 15. Has had lumbar back surgery.

16. [REDACTED]

CLINICAL PROTOCOL

Sponsor: SpineThera Australia Pty Ltd

CLIN-0012-STA01-19 Revision: 06
Effective Date: 17 Jun2020

Page: 39 of 76

19. [REDACTED]

22. Has received an implantable device for pain management

23. [REDACTED]

22 STUDY SCHEDULE AND PROCEDURES

Prior to commencing any study-related procedures it is the Principal Investigator's responsibility to ensure that the study and the Investigational Site has received Ethics approval and Regulatory Authority approval (where relevant) *and* has received written authorization to commence study-related procedures for the Sponsor *and* the Participant Informed Consent Form has been signed by the subject and a study Investigator (who is also a clinician).

Due to the nature of the investigational product and the phase of the study, the Sponsor will review all investigator CVs and the study delegation log prior to commencement of enrolment at each site. Further, diagnostic and pain assessments at Visit 1 and Visit 2 must be performed by an Investigator with Specialist Pain qualifications who has been approved by the Sponsor and delegated to perform these assessments (ie: an approved Investigator). The TF-EI at Visit 2 must be performed by an Investigator who has been approved by the Sponsor and delegated to perform this procedure. Subsequent visits can be performed by other study staff, including general practitioner investigators. Subjects who fail therapy must subsequently be seen by an approved Investigator (Pain Specialist) to ensure that appropriate follow-on clinical care modalities are offered to and made available to this patient.

CLINICAL PROTOCOL

Sponsor: SpineThera Australia Pty Ltd

CLIN-0012-STA01-19 Revision: 06
Effective Date: 17 Jun2020

Page: 40 of 76

CLINICAL PROTOCOL

Sponsor: SpineThera Australia Pty Ltd

CLIN-0012-STA01-19 Revision: 06
Effective Date: 17 Jun2020

Page: 41 of 76

CLINICAL PROTOCOL

Sponsor: SpineThera Australia Pty Ltd

CLIN-0012-STA01-19 Revision: 06
Effective Date: 17 Jun2020

Page: 42 of 76

22.1 Consent

A subject can only consent to participation in this study after all aspects of the study have been explained to the subject, the subject has had adequate time (in their opinion) to consider the information relating to the study and that any questions they may have related to the study are answered adequately. Participation in the study is entirely voluntary and a subject may withdraw consent to participate at any time with no consequences to their standard care regimen provided by their usual treating clinician.

Sponsor and Human Research Ethics Committee approval of the Participant Informed Consent Form (including any required privacy language) is required prior to the enrolment of any subjects in this study. Any changes to the Participant Informed Consent Form language must be approved by the Sponsor and the Human Research Ethics Committee prior to being used to consent or re-consent subjects.

The Investigator must notify all subjects, including completed and withdrawn subjects, of any significant new information that becomes available during the course of the study. All previously consented subjects may be required to consider and provide re-consent.

A subject is considered enrolled in the study when the Participant Informed Consent Form has been signed by the subject and a study Investigator (who is also a clinician).

22.2 Study Visits

Screening: Day -28 to Day -1:

This is the screening visit to determine study eligibility, plus baseline measure of Oswestry Disability Index, and recording of all current treatments (medications, physical therapy etc).

Baseline/Treatment Day 0:

The intervention day when TF-EI is performed, and with 24hr Pharmacokinetic blood sample collections in the assigned subject population.

Follow-up Visits:

Post-dosing at Day 1 and Day 7, a telephone call will review subject status, and seek reporting of any AEs. At Days 14, 30, 60, 90, 120, 150, and 180 post-treatment, the subject will return to the Investigational Site for detailed assessment of both efficacy measures and safety assessments.

[REDACTED]

[REDACTED]

[REDACTED]

[REDACTED]

[REDACTED]

CLINICAL PROTOCOL

Sponsor: SpineThera Australia Pty Ltd

CLIN-0012-STA01-19 Revision: 06
Effective Date: 17 Jun2020

Page: 43 of 76

[REDACTED]

[REDACTED]

[REDACTED]

[REDACTED]

[REDACTED]

CLINICAL PROTOCOL

Sponsor: SpineThera Australia Pty Ltd

CLIN-0012-STA01-19 Revision: 06
Effective Date: 17 Jun2020

Page: 44 of 76

• [REDACTED]

[REDACTED]

• [REDACTED]

[REDACTED]

[REDACTED]

[REDACTED]

[REDACTED]

[REDACTED]

[REDACTED]

CLINICAL PROTOCOL

Sponsor: SpineThera Australia Pty Ltd

CLIN-0012-STA01-19 Revision: 06
Effective Date: 17 Jun2020

Page: 45 of 76

22.2.3.1 TF-EI Procedure

1.

[REDACTED]

NOTE: If injection into an artery has been demonstrated, the procedure should be terminated, and the subject exited from the study. Physicians should not assume that simply repositioning the needle will avoid subsequent intra-arterial injection or uptake of the steroid preparation. The subject may be replaced in the study. The subject will be followed per standard of care.

8.

[REDACTED]

CLINICAL PROTOCOL

Sponsor: SpineThera Australia Pty Ltd

CLIN-0012-STA01-19 Revision: 06
Effective Date: 17 Jun2020

Page: 46 of 76

[REDACTED]

[REDACTED]

[REDACTED]

[REDACTED]

[REDACTED]

[REDACTED]

[REDACTED]

[REDACTED]

CLINICAL PROTOCOL

Sponsor: SpineThera Australia Pty Ltd

CLIN-0012-STA01-19 Revision: 06
Effective Date: 17 Jun2020

Page: 47 of 76

22.2.3.4 Recovery Procedures Post- Epidural Injection

The patient should be transferred to the recovery area, where observations for at least 1 hour including intermittent pulse, respiration, blood pressure monitoring must be completed by a member of the study team.

Prior to discharge, a peripheral neurologic examination of the leg on the side of injection should be conducted by an approved Investigator to exclude any motor weakness, and confirmation of ability to walk and maintain secure balance should be confirmed.

Any complications attributable to, or following, the procedure should be promptly managed in an appropriate manner and recorded in the study documentation (CRF). Once the patient and the physician are satisfied that the patient has suffered no ill-effects, the patient can be discharged after a minimum of 1 hour of observation.

Discharge instructions include:

1. The patient is not to operate a motor vehicle or machinery for the remainder of the day of the procedure, because any numbness due to the local anaesthetic might interfere with their ability to use a pedal.
2. The patient should contact the physician who performed the procedure if they experience any unusual symptoms following the procedure including, but not limited to, headache, fever, chills, increased pain, or paralysis. Contact details must be provided to the patient at the time of discharge.
3. The patient should slowly resume previous activities over a period of several days.
4. Arrange for Visit 3 (14 days +/- 2 from dosing).
5. Instruction for continued daily recording each evening of Worst Daily Leg Pain in the electronic diary.
6. Remind the subject of the telephone call the next day, and again on Day 7 for safety assessment.

22.2.3.5 Procedures for Identifying Inadvertent Administration

Validation of the appropriate position of the needle tip is based on:

1. Absence of flash-back of clear fluid (CSF) or blood in the needle cavity. Further validation can be sought by aspiration of the needle.
2. Interpretation of the radiologic screening of the injection through the needle of a small volume of contrast agent while continuously screening.

CLINICAL PROTOCOL

Sponsor: SpineThera Australia Pty Ltd

CLIN-0012-STA01-19 Revision: 06
Effective Date: 17 Jun2020

Page: 48 of 76

[REDACTED]

[REDACTED]

[REDACTED]

[REDACTED]

[REDACTED]

[REDACTED]

22.2.3.6 Pharmacokinetic Sampling

Following IMP/placebo administration, subjects allocated to the Pharmacokinetic population, will remain in-patient for the scheduled venous blood collection over 24 hours for pharmacokinetic analysis.

After the pre-dose baseline blood sample, post-dose blood samples for the measurement of the dexamethasone concentration in systemic circulation will be collected at the following time-points post-dose: 30, 60, 90 minutes, 2, 4, 6, 8, 12, 20, and 24 hours. Subjects will be discharged from the Investigational Site following collection of the 24 hr PK sample and all 24-hour safety measures (as listed below for other subjects (Telephone call 1) have been conducted and recorded.

Pharmacokinetic sampling is further outlined in Attachment 03 Pharmacokinetic (PK) Laboratory Manual (CLIN-0038).

CLINICAL PROTOCOL

Sponsor: SpineThera Australia Pty Ltd

CLIN-0012-STA01-19 Revision: 06
Effective Date: 17 Jun2020

Page: 50 of 76

[REDACTED]

[REDACTED]

[REDACTED]

[REDACTED]

[REDACTED]

[REDACTED]

CLINICAL PROTOCOL

Sponsor: SpineThera Australia Pty Ltd

CLIN-0012-STA01-19 Revision: 06
Effective Date: 17 Jun2020

Page: 52 of 76

[REDACTED]

[REDACTED]

[REDACTED]

[REDACTED]

[REDACTED]

CLINICAL PROTOCOL

Sponsor: SpineThera Australia Pty Ltd

CLIN-0012-STA01-19 Revision: 06
Effective Date: 17 Jun2020

Page: 53 of 76

22.3 RANDOMISATION

Subjects will be randomly assigned in a 1:1:1 ratio to one of two doses of SX600 (12.5 mg DXA for the low-dose group, or 25.0 mg DXA for the high dose group,) or Placebo (0.9% Sodium Chloride for Injection, BP or equivalent), with a final assignment of 60 subjects/group. The list of randomized treatment assignments will be prepared by statisticians assigned to the study and will be shared with the storage and distribution subcontractor of the study. Additionally, a separate randomisation list known as a kit list will be prepared by the statisticians assigned to the study. The kit list will also be distributed to the storage and distribution subcontractor. The storage and distribution subcontractor will prepare the correctly linked kit number and randomisation number and assign the appropriate IMP to each site. The kit number will be printed on IMP labels and cartons, while the randomisation number will be written in at treatment onto the labels of the IMP. Upon delivery of IMP to sites, there will be a master allocation list with each shipment that links a kit number to a corresponding randomisation number. Each site shall assign an enrolled patient a randomisation number in numerical order. At Visit 2, the unblinded clinician will select the kit number associated with the assigned patient randomisation number and use for injection. The site will not be responsible for randomising treatment groups as each randomisation number that is assigned to each consented patient in the study will already have the treatment selected. The kit number and randomisation number will be recorded in source data.

At the site, the physician who performs the TF-EI will be unblinded to the treatment assignment, but a second physician and study staff who are responsible for all subsequent subject assessments must remain blinded to the treatment assignment. Since the reconstituted active IMP produces an opaque white suspension, it is not possible to blind the injector with a matching placebo solution for epidural administration, and hence 0.9% Sodium Chloride for Injection, BP has been chosen for the placebo comparator.

Randomisation is further outlined in Attachment 04 IMP Randomisation and Shipment Process (CLIN-0037).

22.4 UNBLINDING

Unblinding is allowed where relevant to the acute clinical management of the subject.

The blind may be broken in situations in which the unblinded Investigator (each site must have at least one unblinded Investigator, usually the proceduralist, delegated on the study log) determines that adequate medical care cannot be provided without the knowledge of treatment assignment, or, in situations in which a physician treating a subject cannot contact the unblinded Investigator and then subsequently contacts the Southern Star Research Unblinded Safety Officer. If a code break must occur, the code break may only be undertaken by the unblinded Investigator or the Southern Star Research Unblinded Safety Officer. Contact details for the site and the Southern Star Research Unblinded Safety Officer must be made available to participants eg: using a Participant Identification Card.

Contact Information for Emergency Unblinding

If the blind has been broken, the unblinded Investigator must document the date and the reason the blind was broken in the source notes and CRF.

CLINICAL PROTOCOL

Sponsor: SpineThera Australia Pty Ltd

CLIN-0012-STA01-19 Revision: 06
Effective Date: 17 Jun2020

Page: 54 of 76

22.5 EARLY WITHDRAWAL

Subjects will be encouraged to complete the study and all assessments. A subject may withdraw consent to participate in the study at any time. A subject may be withdrawn from the study for the following reasons:

- Subject withdraws consent
- Subject is lost to follow-up
- Investigator deems early withdrawal necessary
- Other
- Study is terminated

Subjects who withdraw or are withdrawn prior to TF-EI procedure will be replaced. Subjects who withdraw or are withdrawn after IMP administration will NOT be replaced. An Early Withdrawal visit will be completed where possible. Upon withdrawal from the study and completion of the early withdrawal visit, no further study data will be collected, nor study visits occur for the subject. Subjects will be included in analyses up to the time that consent was withdrawn.

If the patient withdraws early the patient should be assessed at the time of withdrawal by an approved Investigator with Specialist Pain qualifications to ensure that appropriate follow-on clinical care modalities are offered to and made available to this patient.

Refer to Section 22.2.12 Early Termination or Subject Early Withdrawal Visit for procedures to be followed if a subject withdraws or is withdrawn from the study.

In the case of subjects who fail to appear for a follow-up assessment, efforts to contact should include at least one telephone call and one letter, which should be documented in the subjects' records. Any additional requirements of the Human Research Ethics Committee should be followed. Lost to follow-up subjects will be withdrawn.

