Adrenocortical suppression with resultant immunosuppression is most likely to occur in patients receiving longer term, high-dose corticosteroid treatment. However, patients receiving moderate doses for short periods, or low doses over a prolonged period, may also be at risk.

Other rare musculoskeletal changes have been associated with corticosteroids, including aseptic necrosis of the femoral and humeral heads, loss of muscle mass, muscle weakness, and osteoporosis with complications in long bones and vertebral compression fractures, steroid myopathy and tendon rupture, mood swings, depression, euphoria, headache, insomnia, neuritis, neuropathy, personality changes and psychic disorders have been associated with corticosteroid use, as has decreased resistance to infection, hiccups, and weight gain.

The information contained in this document is the property of SpineThera Australia Pty Ltd and may not be reproduced, published or disclosed to others without written authorization.

CLINICAL PROTOCOL

Sponsor: SpineThera Australia Pty Ltd

CLIN-0012-STA01-19 Revision: 06
Effective Date: 17 Jun2020

Page: 31 of 76

Because the IMP is a sustained release formulation of a potent corticosteroid (dexamethasone acetate) and the systemic bioavailability of this product is not yet defined in humans, the subject should be notified that any further corticosteroid administration provided as alternative treatment upon withdrawal from the study is not recommended for the duration of the study because of the risk of excessive immunosuppression, and that this must be notified to any subsequent physician referral.

Based on the pre-clinical studies conducted to date, epidural injection of SX600 at the chosen doses and in the restricted lower lumbosacral sites is expected to be well tolerated in humans. Its duration of action in producing pain relief is unknown in humans and will be determined by subject assessment out to 180 days following a single treatment.

For this study, medical imaging must demonstrate a cause of radicular pain and radiculopathy amenable to treatment with transforaminal injection of corticosteroids, such as disc herniation, and must exclude causes for which treatment by injection is not appropriate, such as tumours, cysts, and angiomas. Other causes of axial-derived pain, including clinically significant spinal and foraminal stenosis should be excluded.

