31.3 Data Analysis Populations

The Intent-to-Treat (ITT) population includes all randomized subjects. In the ITT population, subjects will be included in the treatment group to which they were randomized, regardless of treatment received. A safety

The information contained in this document is the property of SpineThera Australia Pty Ltd and may not be reproduced, published or disclosed to others without written authorization.

CLINICAL PROTOCOL

Sponsor: SpineThera Australia Pty Ltd

CLIN-0012-STA01-19 Revision: 06
Effective Date: 17 Jun2020

Page: 73 of 76

analysis will be conducted in the ITT population, which includes patients in which a TF-EI procedure was attempted but abandoned prior to drug delivery and patients who received IMP or placebo, thereby differentiating the effects of the procedure.

The Safety population includes all randomized subjects who proceed to TF-EI (including patients with attempted but halted or failed TF-EI). In the Safety population, subjects will be included in the treatment group based on the treatment that was received. All safety analyses will be conducted in the Safety population.

The modified Intent to Treat population includes all randomized subjects who receive IMP or placebo by TF-EI. This population forms the basis of the primary efficacy and safety analyses. In the mITT population, subjects will be included in the treatment group to which they were randomized, regardless of treatment received. All efficacy analyses will be conducted in the mITT population. The planned enrolment for the study is 180 subjects in the mITT population.

The Per-Protocol (PP) efficacy analysis population includes all randomized subjects who met all inclusion/exclusion criteria; did not have any significant protocol deviations; complied with the assigned study treatment; and either returned to the study site for the Primary Efficacy visit within the specified window, or discontinued study early due to lack of treatment effect or due to receiving therapy other than study specified drug during the study. Supportive efficacy analyses will be conducted in the PP population.

PK population: All subjects who received IMP or placebo and with intensive blood collections in the first 24 hours (approximately 60 subjects). All PK analyses will be conducted in the PK population.

In order to minimize bias, the PP population will be defined prior to unblinding.

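### Protocol 22.5 ends routine safety data collection at any exit, whatever the reason, during the intended release period of a single irreversible injection, and the protocol gives conflicting SAE windows after exit

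*Protocol*

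**What the plan says.** Protocol Section 22.5 lists five reasons for withdrawal: consent withdrawn, loss to follow-up, "Investigator deems early withdrawal necessary", a catch-all category, and study termination. One rule covers all of them: "Upon withdrawal from the study and completion of the early withdrawal visit, no further study data will be collected, nor study visits occur". The early withdrawal visit itself is done only where possible. SAP Section 4 takes data into the analysis up to completion or withdrawal.

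Other sections bear on what happens after exit:

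- **Protocol 23.5.1** requires SAE reporting to 30 days after treatment when the early withdrawal visit falls before Visit 4 (Day 30).
- **Protocol 26.2** requires SAE reporting to 30 days after the last study visit. It also requires every SAE to be followed to an outcome, and suspected related SAEs to be reported whenever the investigator learns of them after the study.
- **Protocol 23.1 and 23.5.5** keep patients who need treatment beyond rescue in safety follow-up.
- **Protocol 22.2.3.1** covers arterial injection: "If injection into an artery has been demonstrated, the procedure should be terminated, and the subject exited from the study". It then says: "The subject will be followed per standard of care".
- **Protocol 31.3** keeps halted or failed procedures in the Safety population. It also plans an ITT safety analysis covering "patients in which a TF-EI procedure was attempted but abandoned prior to drug delivery and patients who received IMP or placebo", in order to separate the effects of the procedure.
- **SAP 9.1** reports AEs as counts and percentages of patients in the Safety population. No person-time display is specified.

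**The concern.** Safety is a primary objective of this first-in-human study (Protocol 18.1). Treatment is a single injection intended to release drug for more than 60 days (Protocol 10 and 19.2), and it cannot be stopped once given. Section 12 says "the systemic bioavailability of this product is not yet defined in humans" and advises against further corticosteroid after withdrawal for the duration of the study. The protocol therefore recognises that exposure may continue after exit, yet Section 22.5 ends routine observation of it, including for patients who never asked for data collection to stop.

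An AE percentage on the full Safety population treats a patient seen for 14 days like one seen for 180. An AE that starts after an early exit and is not serious will not be recorded, and the patient stays in the denominator. Percentages then understate 180-day incidence. If exits differ between arms in number or timing, the comparison between arms is distorted as well.

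**Working it through.** **The plan's own figures.** The documents state no withdrawal rate and no expected person-time, so there is no plan figure to reproduce on this point. Their only design calculation is power: 94% for 50% against 20%, and 81% for 50% against 25%, at 60 per arm. A pooled-variance normal approximation at two-sided 0.05 gives 94.1% and 81.6%. The present point does not depend on it.

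**Step 1: follow-up by exit day.** Inputs are 180 days of planned follow-up (Protocol 15 and 19.1) and the stop rule in 22.5. Share of AE follow-up obtained = exit day / 180. For the SAE windows I assume that the early withdrawal visit takes place on the exit day and counts as the last study visit.

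| Exit day | AE follow-up obtained | SAE reporting ends, 23.5.1 | SAE reporting ends, 26.2 |
|---|---|---|---|
| 0 | 0% | Day 30 | Day 30 |
| 14 | 14/180 = 7.8% | Day 30 | 14 + 30 = Day 44 |
| 30 | 30/180 = 16.7% | no window given | Day 60 |
| 60 | 60/180 = 33% | no window given | Day 90 |
| 90 | 90/180 = 50% | no window given | Day 120 |
| 150 | 150/180 = 83% | no window given | Day 180 |

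For a Day 14 exit the two SAE windows cover 30/180 = 17% and 44/180 = 24% of planned follow-up. For any exit before Day 30, both close before Day 60, while release is intended to last longer than that. If no early withdrawal visit takes place, the 26.2 window runs from an earlier visit and closes sooner.

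**Step 2: person-time lost.** Let w be the proportion who exit. Loss = w × (1 − mean exit day / 180). The documents do not give w, so I assume 5% to 20%.

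- Exits spread evenly over 180 days (mean Day 90): loss = 0.5w, which is 2.5% to 10%.
- All exits at Day 14: loss = w × 166/180 = 0.922w, which is 4.6% to 18.4%.

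With the 55 treated patients in SAP 3.1, planned follow-up is 55 × 180 = 9,900 person-days. At w = 20%, 11 patients exit. The loss is 11 × 90 = 990 days (10%) if evenly spread, or 11 × 166 = 1,826 days (18.4%) if all exit at Day 14.

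**Step 3: passages side by side.** Section 22.5 says that no study data are collected after exit. Sections 23.5.1 and 26.2 require SAE data after exit, with different end dates. SAP Section 4 does not say whether an SAE reported after exit enters the tables. Separately, 22.2.3.1 sends a patient with arterial injection out of the study to standard of care, while 31.3 relies on halted procedures to separate procedure effects. Neither section says what safety data those patients should contribute.

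**The case against.** The strongest reply is that the protocol protects patients better than the sentence in 22.5 suggests, and much of this stands.

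- **A reader might infer that all data collection ends at exit.** It does not. SAE reporting, SAE follow-up to outcome and late reporting of related SAEs continue (23.5.1, 26.2). Section 23.5.1 can also be read as following ongoing AEs until they settle. What stops is routine collection.
- **A reader might infer that exiting patients in general have little or no follow-up.** That fits early exits only; a Day 150 exit retains 83%.
- **A reader might apply the continuing-release argument to arterial injections.** Needle position is checked with contrast (22.2.3.5), and 31.3 describes procedures abandoned before drug delivery, so some of these patients have no depot. For them the issue is the procedure analysis alone.
- **A reader might conclude that procedure effects cannot be studied in halted patients.** Complications of the procedure are recorded on Day 0 (22.2.3.4), AE collection starts at Visit 2, and SAP 6.8 tabulates attempted, halted and failed procedures. Acute effects are observable; later ones are not covered by study visits. The group may also be empty: SAP 3.1 gives 55 treated and SAP 3.3 gives 55 randomized.
- **A reader might assume that the sickest patients are the ones lost.** The documents do not show this. Patients treated beyond rescue stay in safety follow-up, and no visible passage makes an AE a trigger for withdrawal.

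Section 22.2.12, to which 22.5 refers for withdrawal procedures, is redacted, as are most steps of 22.2.3.1. Further safety contact could be specified there. The sentence in 22.5 is nevertheless explicit and makes no exception. SAP 6.2 reports disposition with reasons and SAP 9.1 reports TEAEs leading to withdrawal, but neither shows how long each arm was observed.

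**Conclusion.** The point holds in a limited form. Section 22.5 stops routine safety data at every exit without separating withdrawal of consent from other reasons, in a first-in-human study of a product whose exposure continues after exit. The three statements on collection after exit (22.5, 23.5.1, 26.2) do not agree. For exits before Day 30, both SAE windows close before the intended release is over.

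The loss of AE person-time is 2.5% to 10% for evenly spread exits and 4.6% to 18.4% if all exits fall at Day 14. Both ranges rest on an assumed exit rate of 5% to 20%, because the documents give none. The size of any bias in the AE percentages, and whether it differs by arm, cannot be derived from the documents. The redaction of 22.2.12 limits certainty about what is done in practice.

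**What to change.** 1. **Protocol 22.5.** Separate leaving study visits from withdrawing consent to data collection. For exits other than consent withdrawal or loss to follow-up, continue collecting AEs and concomitant treatment to Day 180 by visit or telephone. Sections 23.1 and 23.5.5 already do this for patients treated beyond rescue. SAP Section 4 needs a matching line so that these data enter the tables.
2. **Protocol 22.5, 23.5.1 and 26.2.** Reconcile what SAE data are collected after exit and for how long.
3. **Protocol 22.2.3.1 and 31.3.** Reconcile the exit of patients with arterial injection with the use of halted procedures in the safety analyses, as to which safety data are collected. Clinical management is not changed.
4. **SAP 9.1.** Show person-days of follow-up by arm with the AE tables.

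The cost is protocol wording and some telephone contacts by existing staff for a few patients. Enrolment has stopped at 55, so the collection change helps only patients still in follow-up. The person-days display needs only treatment and exit dates and remains fully feasible.
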